8 SAFETY ASSESSMENTS

8.1 Adverse Events

All clinical adverse events occurring after the subject signs the ICF and up to 4 weeks after the last dose of study medication, whether observed by the investigator or reported by the subject, will be recorded on the Adverse Event CRF page. All serious adverse events (SAEs) are to be reported according to the procedures in Section 8.3 SAE Reporting-Procedure for Investigators. In addition, any untoward event that may occur subsequent to the reporting period that the Investigator assesses as related (definitely, possibly or probably) to study drug should also be reported and managed as an AE. Pre-planned procedure or hospitalization for pre-existing conditions which do not worsen in severity should not be reported as SAEs (see Section 8.1.1 for Definitions).

At each visit, the investigator will determine whether any adverse events have occurred by evaluating the subject. Adverse events may be directly observed, reported spontaneously by the subject or by questioning the subject at each study visit. Subjects should be questioned in a general way, without asking about the occurrence of any specific symptoms. All laboratory values must be appraised by the Investigator as to clinical significance. All post-baseline abnormal laboratory values considered clinically significant by the Investigator must be recorded in the adverse event page of the CRF.

Investigator should follow subjects with adverse events until the event has resolved or the condition has stabilized. In case of unresolved adverse events including significant abnormal laboratory values at the end of study assessment, these events will be followed up until resolution or until they become clinically not relevant.

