After informed consent during screening any clinically significant abnormality which meets the definition of AE should be recorded as a pre-treatment AE prior to the use of the product (Day 1) and should be recorded accordingly. Any new clinically significant event or worsening of existing medical history condition, which meets the definition of AE prior to the application of IP will also be considered as pre-treatment adverse event.

Post-treatment Adverse Events

All AEs recorded after the first dose of IP (Day 91) till the end of treatment will be considered as post-treatment AEs. Disease signs, symptoms and/or laboratory abnormalities already existing prior to the use of the product will not be considered as adverse experiences after treatment (post-treatment AEs) unless they reoccur after the subject/patient has recovered from the pre-treatment condition or they represent an exacerbation in intensity or frequency or the character of the condition worsens during the study period.

General Physical Examination Findings

At screening, any clinically significant abnormality should be recorded as a pre-existing condition. At the end of the study, any new clinically significant findings/abnormalities that meet the definition of an adverse event must also be recorded and documented as an adverse event.

Post-study Adverse Event

At the last scheduled visit, the investigator should instruct each subject to report any subsequent event(s) that occur within 14 days after discontinuation of treatment. The investigator should notify the sponsor of any death or adverse event occurring at any time after a subject has discontinued or terminated study participation that may reasonably be related to this study.

Abnormal Laboratory Values

A clinically significant laboratory abnormality should be documented as an adverse event if any one of the following conditions is met:

- The laboratory abnormality is not otherwise refuted by a repeat test to confirm the abnormality
- The abnormality suggests a disease and/or organ toxicity, then the underlying condition should be captured as an AE.
- The abnormality is of a degree that requires active management; e.g. change of dose, discontinuation of the drug, more frequent follow-up assessments, further diagnostic investigation, etc.

Lab abnormalities found during the screening tests will not be considered as adverse event.

Hospitalization, Prolonged Hospitalization or Surgery

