Any adverse event that results in hospitalization or prolonged hospitalization should be documented and reported as a serious adverse event. Any condition responsible for surgery should be documented as an adverse event if the condition meets the criteria for an adverse event.

Neither the condition, hospitalization, prolonged hospitalization, nor surgery are reported as an adverse event in the following circumstances:

- Hospitalization or prolonged hospitalization for diagnostic or elective surgical procedures for a pre-existing condition. Surgery should not be reported as an outcome of an adverse event if the purpose of the surgery was elective or diagnostic and the outcome was uneventful.
- Hospitalization or prolonged hospitalization required to allow efficacy measurement for the study.
- Hospitalization or prolonged hospitalization for therapy of the target disease of the study, unless it is a worsening or increase in frequency of hospital admissions as judged by the clinical Investigator.

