8.9 Other Safety Assessments

The most frequent adverse drug reaction during treatment with epoetin is a dose-dependent increase in blood pressure or aggravation of existing hypertension. Special care should be taken to closely monitor and control blood pressure in subjects treated with epoetin. If blood pressure is difficult to control after initiation of appropriate measures, the dose of epoetin should be reduced or temporarily withheld until haemoglobin begins to decrease. An increased incidence of thrombotic vascular events has been observed in patients receiving epoetin. These include venous and arterial thrombosis and embolism (including some with fatal outcomes), such as deep venous thrombosis, pulmonary emboli, retinal thrombosis and myocardial infarction.

Hence adverse events of specific interest include hypertension/aggravation of hypertension and thromboembolic events.

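### The hospitalisation exemption in 8.1.1.2 conflicts with the protocol's own adverse-event rules for a pre-existing condition that worsens and leads to a diagnostic or elective surgical admission

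*Protocol*

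**What the plan says.** Protocol 8.1 sets a narrow exemption: "Pre-planned procedure or hospitalization for pre-existing conditions which do not worsen in severity should not be reported as SAEs". A note in 8.1.1.2 repeats it in nearly the same terms. Both require that the admission was planned beforehand and that the condition has not worsened, and both exempt from serious adverse event (SAE) status only.

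The definition in 8.1.1.1 covers illness that appears or worsens during the trial. The post-treatment rule in 8.1.1.2 leaves out problems that existed before the product was used, unless they recur after recovery or "they represent an exacerbation in intensity or frequency or the character of the condition worsens during the study period".

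The part of 8.1.1.2 on hospitalisation and surgery starts with two inclusive rules: "Any adverse event that results in hospitalization or prolonged hospitalization should be documented and reported as a serious adverse event" and "Any condition responsible for surgery should be documented as an adverse event if the condition meets the criteria for an adverse event". It then turns to exceptions: "Neither the condition, hospitalization, prolonged hospitalization, nor surgery are reported as an adverse event in the following circumstances". The first exception is "Hospitalization or prolonged hospitalization for diagnostic or elective surgical procedures for a pre-existing condition". The second concerns admissions needed for efficacy measurement and is not at issue. The third concerns therapy of the target disease and carries a limit: "unless it is a worsening or increase in frequency of hospital admissions as judged by the clinical Investigator".

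Section 8.9 ends: "Hence adverse events of specific interest include hypertension/aggravation of hypertension and thromboembolic events".

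**The concern.** The lead-in to the exception list differs from the exemption in 8.1 in three ways. It names the condition as well as the admission. It works at the level of the adverse event (AE), not only the SAE. Its first item requires neither prior planning nor absence of worsening. Because the third item does carry a worsening limit, a site may reasonably conclude that the first was meant to have none.

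Incidence and nature of adverse events is a safety endpoint (3.1.3, 9.5). Aggravation of hypertension is by definition the worsening of something already present, so it belongs to the class of event that the first item can reach. Section 8.9 also names a rise in blood pressure or aggravated hypertension as the most frequent adverse reaction to epoetin. With centres in Thailand and Russia, two sites relying on different sentences of the same section could record the same event differently.

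**Working it through.** No arithmetic applies. The check is to take each kind of case and ask what every rule says about it.

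**Case 1: pre-existing condition, not worsened, admitted for a diagnostic or elective surgical procedure.**
- 8.1.1.1 and the post-treatment rule: nothing has appeared or worsened, so there is no AE.
- 8.1 and the note in 8.1.1.2: not an SAE if pre-planned.
- First item of the exception list: not reported.
- Result: the rules agree.

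**Case 2: pre-existing condition that worsens on study and leads to admission for a diagnostic or elective surgical procedure.**
- 8.1.1.1: an AE, because it worsened.
- Post-treatment rule in 8.1.1.2: an AE, because it is an exacerbation.
- Opening of the hospitalisation part of 8.1.1.2: documented as an AE when it leads to surgery, and an SAE when it results in admission.
- 8.1 and the note in 8.1.1.2: the exemption is not available, because the condition worsened.
- First item of the exception list: read literally, neither the admission nor the condition is reported.
- Result: direct conflict. The same event is an SAE under one set of sentences and no event at all under another.

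**Case 3: new condition on study, such as new hypertension, a new thromboembolic event or a new access obstruction.**
- 8.1.1.2 treats a medical history condition as one already present at screening. An access that exists at screening is not the same as an obstruction of it that arises later.
- First item of the exception list: does not apply, because the condition is not pre-existing.
- Result: reportable under all the rules, and an SAE if it leads to admission.

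**Case 4: worsened pre-existing condition, unplanned admission for treatment.**
- First item: does not plainly apply, because the admission is not for a diagnostic or elective surgical procedure.
- Third item, if the treatment is for the target disease: its own worsening limit keeps the event reportable when the investigator judges it worse.
- Result: no clear conflict.

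The contradiction is therefore confined to Case 2. Its direct opponents are the definition in 8.1.1.1, the post-treatment rule and the opening sentences of the same part of 8.1.1.2. The mismatch with 8.1 is indirect, since 8.1 deals with pre-planned procedures and SAE status.

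**The case against.** The strongest reply is that the protocol already keeps worsened conditions reportable. The sentence just before the exception list makes a condition that leads to surgery an AE if it meets the criteria, and a note earlier in 8.1.1.2 says that the reason for a procedure may be an AE. The follow-on sentence in the first item concerns surgery as an outcome, which suggests that the authors had the procedure in mind rather than the condition. The item also never says that worsened conditions are exempt; that is inferred from silence.

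This stands in part. It shows that the intention was probably narrower than the words, and that the defect is a contradiction rather than a settled rule that removes worsened conditions. It does not cure the defect. The list comes after the inclusive sentences, reads as an exception to them and expressly names the condition, so a site cannot obey both.

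A second reply concerns blood pressure. Section 8.6 collects vital signs at every visit and has clinically significant changes recorded as AEs, with no exception for hospitalised subjects. Section 8.8 does the same for physical findings, and 14.2 has the investigator record all AEs. This stands as mitigation: aggravated hypertension has another way into the record. It does not settle which rule governs when the subject is admitted, nor whether the event is then also an SAE.

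A reader might infer that the list generally strips out events of specific interest, including thrombosis and fistula obstruction, or the more serious cases of them. The documents do not support that. New events are outside the first item, and unplanned admissions for an AE remain SAEs. A reader might also want to express the loss as reduced power to see a difference between arms. That would need an event rate and a share of events falling under the list. The protocol gives neither, and its safety analysis is descriptive.

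**Conclusion.** The point holds for one case: a pre-existing condition that worsens on study and leads to admission for a diagnostic or elective surgical procedure. For that case 8.1.1.2 contradicts 8.1.1.1, its own post-treatment rule and its own opening sentences on hospitalisation. Followed literally, it leaves an AE, and an SAE, unreported.

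The likely consequence is omitted or inconsistent recording of some aggravations of pre-existing conditions, possibly including aggravated hypertension, with 8.6 as a partial safeguard. The size cannot be stated from the documents and may be small. The conclusion rests on a literal reading of the exception list and on sites treating it as overriding the sentences before it. It needs no assumption about event rates. The correction is worth making because the affected data feed a stated safety endpoint and the change is nearly free.

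**What to change.** Reconcile the hospitalisation part of 8.1.1.2 with 8.1, 8.1.1.1 and the rest of 8.1.1.2 by two edits:

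1. Limit the first item to pre-planned admissions or procedures for a pre-existing condition that has not worsened. This uses the limits that 8.1 already sets.
2. Reword the lead-in so that only the admission or procedure is exempt, and add that a new or worsened condition behind it is reported as an AE, and as an SAE if it led to hospitalisation.

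Any site guidance on completing the adverse-event pages should carry the same wording. A separate list of events that must always be reported is not needed to cure this defect.

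The cost is a short text change and a few more AE and SAE forms. Cases where the condition has not worsened are handled as before.

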8.1.1.3 AE Severity

The following definitions should be used to assess intensity of adverse events:

- Mild: Symptom(s) barely noticeable to subject or does not make subject uncomfortable; does not influence performance or functioning; prescription drug not ordinarily needed for relief or symptom(s) but may be given because of personality of subject.
- Moderate: Symptom(s) of a sufficient severity to make subject uncomfortable; performance of daily activity is influenced; subject is able to continue in study; treatment for symptom(s) may be needed.
- Severe: Symptom(s) cause severe discomfort; symptoms cause incapacitation or significant impact on subject's daily life; severity may cause cessation of treatment with study treatment; treatment for symptom(s) may be given and/or subject hospitalization.

8.1.1.4 Causality Assessment

The relationship between an adverse event and the study product will be determined by the investigator on the basis of his/her clinical judgment and the following definitions:

- Definite: Causal relationship is certain. E.g. reasonable temporal relationship between drug exposure and AE, clinically compatible response to dechallenge, other causes eliminated, rechallenge response present definitive pharmacologically
- Probable: High degree of certainty for causal relationship. E.g. high degree of temporal relation between drug exposure & AE onset/course, clinically compatible response to dechallenge, other causes eliminated

- Possible: Causal relationship is uncertain /does not appear probable. Has a temporal relationship to the drug exposure but not a known or reported response to the drug, may be attributed to other causes also
- Unlikely: not reasonably related, however causal relationship can't be ruled out
- Not Related: No possible relationship, Causal relationship to study drug impossible

8.1.1.5 Action Taken Regarding the Study Product

1 = None

No change in study drug dosage was made.

2 = Discontinued Permanently

The study product was permanently stopped.

3 = Reduced

The dosage of study product was reduced.

4 = Interrupted

The study product was temporarily stopped.

5 = Increased

8.1.1.6 Adverse Event Outcome

1 = Recovered/Resolved

The subject fully recovered from the adverse event with no residual effect observed.

2 = Recovered/Resolved with Sequelae

The residual effects of the adverse event are still present and observable.

Identify sequelae/residual effects.

3 = Not Recovered/Not Resolved

The adverse event itself is still present and observable.

4 = Fatal

5 = Unknown

8.1.1.7 Other Action Taken for Event

1 = None.

2 = Medication required.

Prescription and/or Over the Counter (OTC) medication was required to treat the adverse event.

3 = Hospitalization or prolongation of hospitalization required.

Hospitalization was required or prolonged due to the adverse event, whether or not medication was required.

4 = Other.

8.2 Expected Adverse Events

The expected adverse events with the study drug are the following:

- Local pain
- Hypertension
- Headache
- Fever
- Skin rash
- Dizziness / hypodynia
- Local swelling
- Internal fistula obstruction
- Arthralgia
- Abdominalgia
- Nausea/vomiting
- Muscle pain
- High blood viscosity
- Epilepsy
- Stuffy nose
- Thrombosis
- Cerebral hemorrhage
- Diarrhoea
- Hyperkalemia
- PRCA

Preventive action for subject developing PRCA:

- Perform Anti- epoetin Antibody test at screening visit
- All high-risk patients will be excluded as per the inclusion and exclusion criteria.

- Performing regular test of immunogenicity at visit 5, 8, 11, 13, 16 and 23 to detect development of Anti- epoetin Antibody

Corrective action for patients developing PRCA:

- If immunogenicity test is positive, the epoetin treatment will be stopped and appropriate treatment will be provided to subject including kidney transplant. Cost of treatment will be supported by sponsor.

8.3 Serious Adverse Event Reporting Procedure for Investigators

8.3.1 Initial Reports

An event that is serious must be recorded on the SAE page of the CRF and requires expeditious handling and reporting to EA and the sponsor to comply with regulatory requirements.

A SAE, regardless of its relation to the study drug, must be reported to the study medical monitor EA by telephone or email within 24 hrs of the knowledge of event and the SAE form should be completed and faxed/mailed to the study medical monitor EA and Pharmacovigilance (PV) Cell within 24 hrs. Report serious adverse events by phone and facsimile to: **Medical Monitor**

[name]

Ecron Acunova Ltd.

[name],

[name]

[contact]

[contact]

Mob: [name]

Email: [contact]

[contact]

During this time a completed written report (SAE report form) must be completed and submitted (faxed or mailed) by the Investigator. For all SAEs, a SAE Report Form will include a detailed written description, copies of relevant subject/patient records, autopsy reports when available, and other documents which will be sent to EA medical monitor and PV cell within 24 hours. The causality assessment to the study medication should always be included. The investigator must complete, sign and date the SAE form, verify the accuracy of the information recorded on the SAE pages with the corresponding source documents, and send a copy (by fax/email) to EA monitor and PV Cell. The SAE information will be forwarded to the sponsor, within 24 hrs of knowledge of the event by EA / PV cell.

The PI will keep a copy of the SAE form in file at the study site. The subject identity should not be disclosed by the investigator while reporting SAE, unless specifically asked by the regulatory body or ethics committee. In case of emergency or occurrence of SAE, which requires unblinding of study medication for a subject, investigators will be able to access this information via IVRS/IWRS (see section 5.1.6).

All SAE communications and pregnancy notifications will be forwarded to the sponsor by EA /PV Cell within 24 hours of the knowledge of the event, by confirmed facsimile transmission or mailing of the completed SAE page. A facsimile transmission does not preclude mailing of the SAE page. At the time of the initial report, the following information should be provided:


• Subject Initials• Subject number• A description of SAE
– Date of onset– Current status– De-challenge and re-challenge information (if applicable)– Setting– Outcome• Investigator assessment of the association between the event and drug	
• Suspected drug details:
– Generic name– Indications– Dosage of the drug administered to the subject– Route of administration– Start and stop date and time.• Other treatments• Details of the Investigator
--	---

8.3.2 Follow-up Reports

Significant new/follow-up information on ongoing SAE (hospital discharge summaries, operative reports etc.) should be sought after and a follow-up SAE form should be completed and submitted promptly to the Medical Monitor and PV Cell within same 24 hours deadline from the time of receipt of the information. A designation of causality from the study medication should always be included with a follow up report. All follow-up SAE reports will also be forwarded to the Sponsor within 24 hrs of PV cell receiving the information.

8.3.3 Notifying Investigators or Ethics Committee/Institutional Review Board

Sponsor and/or EA will undertake to inform Investigators of any serious, unexpected (not listed in the Investigator's Brochure) and related AEs occurring in other study centers or other studies of the investigational product, as appropriate.

Reports of all SAE (and follow-up information) must be submitted to the IEC of the site where the SAE occurred within 7 working days of occurrence of event. It is the responsibility of the PI to notify the IEC. Copies of each report and documentation of IEC notification and acknowledgement receipt will be kept in the investigator site file and the same will be sent to EA medical monitor and PV Cell EA by fax or email.

8.3.4 Regulatory Notification by Ecron Acunova Ltd

All SAEs including the suspected unexpected serious adverse reactions (SUSAR) (as defined in GCP Guidelines) occurring during the clinical trial will be communicated to applicable regulatory agency within 7 calendar days for AEs which are result in death/be life-threatening and within 15 days for AEs that are not life-threatening and to the other Investigator (s) participating in the study within the applicable timelines by the EA as per EA's SOPs.

If a previous AE(s) that was not initially deemed reportable is later found to fit the criteria for reporting, EA will submit the adverse event in a written report to the applicable regulatory agency as soon as possible, but no later than 15 calendar days from the time the determination is made.

8.4 Exposure in Utero during Clinical Studies

If a subject becomes pregnant any time after receiving a study treatment, she must not receive additional study treatment and must be discontinued from the study. The subject must be followed until the outcome of the pregnancy is known (i.e., delivery, elective termination, or spontaneous abortion). If the pregnancy results in the birth of a child, additional follow-up information may be requested.

The Investigator must notify EA within 24 hours of first learning of the occurrence of pregnancy using the Pregnancy Notification Form and faxing it to EA providing as much information as possible. The Investigator must notify EA about reported complications within 24 hours using the same procedure. Outcome of pregnancy once known by the Investigator must also be reported to EA within 24 hours using the Pregnancy Outcome Form and faxing it to EA. Pregnancy communications will be directed to:

Ecron Acunova
[contact]

Please note that pregnancy in and of itself is not an AE or SAE. Pregnancy should not be entered into the CRF as an AE unless the Investigator suspects an interaction between the study treatment and contraceptive method. Pregnancy will be documented as the reason for study discontinuation.

EA will direct the pregnancy communication to sponsor as soon as they are received.

